### **Safety**

Safety data will not be formally analyzed. All subjects who receive at least one dose of ibrutinib or pembrolizumab will be included in the assessment of the safety profile (safety analysis set). At the end of the study, appropriate summaries of all safety data will be produced, as defined below.

Data from all cycles of initial treatment will be combined in the presentation of safety data. AEs will be listed individually by subject and dose group/expansion phase arm. For subjects who have a dose modification, all AEs (due to drug or otherwise) will be assigned to the initial dose group. The number of subjects experiencing each AE will be summarized by the Medical Dictionary for Regulatory Activities (MedDRA) system organ class, MedDRA preferred term and CTCAE grade. The number and percentage of subjects with adverse events in different categories (e.g., causally related, CTCAE grade  $\geq 3$  etc.) will be summarized by dose group/expansion phase arm, and events in each category will be further summarized by MedDRA system organ class and preferred term, by dose group. SAEs will be summarized separately if a sufficient number occur.

Any AE occurring before the first dose of investigational product (i.e., before study Day 1) will be included in the data listings but will not be included in the summary tables of adverse events.

Any AE occurring within the defined 30 day follow-up period after discontinuation of investigational product will be included in the AE summaries. AEs occurring after the 90 day follow-up period after discontinuation of investigational product will be listed separately, but not included in the summaries. Hematology, clinical chemistry, vital signs, ECG data, urinalysis, demographic data, medical histories and concomitant medications will be listed individually by subject and suitably summarized. For all laboratory variables, which are included in the current version of CTCAE, the CTCAE grade will be calculated. Summary statistics of mean, median, standard deviation, minimum, maximum and number of observations will be used. Details of any deaths will be listed for all subjects. Any qualitative assessments will be summarized for all subjects using the number of subjects with results of negative, trace or positive. Graphical presentations of safety data will be presented as is deemed appropriate. This may include, but is not restricted to, presentation of parameters against time, concentration or shift plots. Appropriate scatter plots will also be considered to investigate trends in parameters compared to baseline.

### **Tumor response**

Tumor response data will be summarized for dosed subjects with measurable disease at baseline.

Objective response rate, disease control rate and PFS will be summarized in the expansion phase arm.

Tumor response will be analyzed using RECIST 1.1 criteria (Appendix B) and the immune response criteria. Confirmation of immune response will be done at the discretion of the investigator.

In this classification, the overall response is determined as follows:

- Immune response CR (irCR) is a complete disappearance of all lesions (whether measurable or not, and no new lesions) with confirmation by a repeat, consecutive assessment no less than 4 weeks from the first documentation.
- Immune response PR (irPR) is a decrease in tumor burden of greater than or equal to 50% relative to baseline. This must be confirmed by a consecutive assessment at least 4 weeks after the first documentation.
- Immune response SD (irSD) is classified as those who do not meet criteria for irCR or irPR and who do not have irPD
- Immune response PD (irPD) is an increase in tumor burden of greater than or equal to 25% relative to the minimum recorded tumor burden which must be confirmed by a repeat, consecutive assessment no less than 4 weeks from the first documentation.

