#### **4.3.2 Removal of Patients from Protocol Therapy**

Patients will be removed from study when any of the criteria listed

- Disease progression
- Intercurrent illness that prevents further administration of treatment
- Unacceptable AE(s)
- Patient decides to withdraw from the study **OR**
- General or specific changes in the patient's condition render the patient unacceptable for further treatment in the judgment of the investigator

Notify the Principal Investigator and document the reason for study removal and the date the patient was removed in the eCRF. The patient should be followed per protocol

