- h. Hepatitis B surface antigen, surface antibody, and Hepatitis C antibody
- i. Pregnancy test will be performed at baseline for WOCBP and then only as clinically indicated
- j. After off treatment following disease progression survival f/u, can be performed over the phone every 3 months
- k. Archival tissues ( 10 unstained slides) if available
- l. The PBMC should be viably frozen (for flow cytometric analysis) and the plasma frozen separately .The actual analyses used will be based on response and determined by the investigator at a later date. Two green top (Sodium Heparin) tubes (about 20 ml) will be used each time. This will ONLY be collected at the screening and at the beginning of the 3rd cycle.
- m. If a subject discontinues treatment due to confirmed PD, only the EOT disease assessment is required if it has been > 4 weeks since the last disease assessment
- n. The safety follow-up visit will be approximately 30 days after the last dose or prior to the start of a subsequent anti-cancer therapy.

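### Section 9.7 makes irRC confirmation both optional and required, and a first progression that is never rescanned is classified irSD, which can distort the secondary irRC results

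*Combined protocol and SAP*

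**What the plan says.** Section 9.7 (Tumor response) introduces the irRC analysis with "Confirmation of immune response will be done at the discretion of the investigator". The definitions that follow do not leave it open:

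- irCR is defined "with confirmation by a repeat, consecutive assessment no less than 4 weeks from the first documentation".
- For irPR: "This must be confirmed by a consecutive assessment at least 4 weeks after the first documentation".
- irPD is an increase of at least 25% over the minimum recorded burden, "which must be confirmed by a repeat, consecutive assessment no less than 4 weeks from the first documentation".
- The remaining class is residual: "Immune response SD (irSD) is classified as those who do not meet criteria for irCR or irPR and who do not have irPD".

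Section 9.6 has a program assign each visit one of four values (CR, PR, SD, PD) under both RECIST and irRC. There is no unconfirmed or not-evaluable value.

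On what happens at progression, Section 4.3.2 says "Patients will be removed from study when any of the criteria listed" are met, and disease progression is the first item. Section 4.3 takes progressing patients off treatment unless the principal investigator judges that they are benefiting. Footnote m of the Section 6.6 calendar covers patients who stop because of *confirmed* PD and says "only the EOT disease assessment is required if it has been > 4 weeks since the last disease assessment". Section 6.5 starts telephone survival follow-up after *confirmed* progression or new anti-cancer therapy.

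irRC efficacy is a numbered secondary objective for phase I (Section 2), and irRC tumor response is a secondary endpoint with no phase named (Section 9.1).

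**The concern.** There are two linked defects. First, the discretion sentence and the definitions cannot both govern: a repeat assessment is either a condition of the category or it is optional. The trial is open-label and single-arm, so the investigator knows the first scan when deciding whether to obtain a second, and the irRC category can depend on that decision.

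Second, because irPD exists only once confirmed and irSD takes everyone left over, a patient who progresses on one scan and has no other is recorded as stable. A summary that counts irSD as disease control would then count that patient as controlled.

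At stake is whether the secondary irRC results can be read at face value, or set beside the RECIST 1.1 results as a comparison of criteria.

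**Working it through.** The plan gives no numerical figure for irRC, so the main check is on the text.

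**1. Classify a patient with one scan showing an increase of at least 25% and no later scan.**
- irCR: no, lesions remain.
- irPR: no, there is no decrease of 50%.
- irPD: no, the repeat assessment is missing.
- irSD: yes, since none of the other three applies.
- Any other value: none is available under Section 9.6.

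Programmatic assignment does not help, because the program would apply this same rule.

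**2. Can such a patient arise?**
- Sections 4.3 and 4.3.2 act on progression and do not require that it be confirmed.
- The calendar schedules tumor assessment at screening, every third cycle and EOT only. Nothing is scheduled at the safety visit or in post-progression follow-up.
- A patient whose EOT visit falls within 4 weeks of the scan showing progression has no further scan called for.

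**3. Who would be rescanned?**
- Patients whose EOT visit comes more than 4 weeks after the last scan. That scan meets the 4-week minimum. (Footnote m calls it required; Section 6.5 says it may be done.)
- Patients kept on treatment for benefit. On-treatment scans are 3 cycles × 3 weeks = 9 weeks apart, which also meets the minimum.
- Patients scanned when clinically indicated (calendar footnote c).

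The gap therefore mainly concerns patients who stop promptly at first progression.

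**4. Size per patient.** With denominator n, each misplaced patient adds 1/n to an irRC disease control proportion.
- n = 32 (planned phase II number): 1/32 = 3.1 points; 2/32 = 6.3; 3/32 = 9.4; 4/32 = 12.5; 5/32 = 15.6. These counts are assumptions. As a yardstick only, the design rates of 5% and 20% in Section 9.2 are 15 points apart.
- Smaller n: Section 9.7 limits tumor response to dosed patients with measurable disease, while Section 4.1 admits non-measurable disease, so n may be below 32. At an assumed n of 24, one patient is 1/24 = 4.2 points.
- Phase I (6 to 12 patients in the synopsis): 1/12 = 8.3 to 1/6 = 16.7 points.

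**5. Direction.** Disease control under irRC moves up. Objective response can move either way: up if discretion is taken to waive confirmation of irCR and irPR, down if the definitions are enforced but no repeat scan is obtained.

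**6. Primary design.** Success probability = Σ over x ≥ 1 of P(Bin(18, p) = x) × P(Bin(14, p) ≥ max(0, 4 − x)). This gives 0.072 at p = 5% (limit 0.10) and 0.901 at p = 20% (target 0.90). The stated design reproduces, and nothing here alters it.

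**The case against.** The strongest reply has four parts.

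*The schedule presumes confirmation.* Footnote m and the telephone follow-up apply after confirmed progression, so they cannot be cited as showing that unconfirmed progressors go unscanned. This stands. What remains is that the rules which actually stop treatment do not ask for confirmation, no visit supplies it, and those two places do not define the term. The gap is possible, not shown to be usual.

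*Discretion may govern only the ordering of the scan, with the definitions governing classification.* This is a fair reading and would remove inflation of irCR and irPR. It does not cure the defect: classification would still depend on whom the investigator chose to rescan, and an unconfirmed progressor would still land in irSD.

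*The plan never names an irRC disease control rate.* True: Sections 3, 9.1 and 9.2 define disease control as CR + PR + SD. But Section 9.7 summarizes disease control for the expansion arm and analyzes response by both criteria, so an irRC version is a natural output. The irSD category itself is wrong for these patients in any case.

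*The effect may be small.* It may. A reader might go the other way and infer that, with 5% to 20% true control, nearly all of the 32 patients could be counted as controlled under irRC at 4 months. The documents do not support that. They give no rate of unconfirmed irPD, some patients will be rescanned, the denominator need not be 32, and visit-based assignment gives no 4-month response to a patient who left earlier. The default acts on the earlier visit or on best response. Nor do the documents show that any investigator would confirm selectively; they only leave room for it.

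**Conclusion.** The point holds as a defect in the secondary irRC analysis. Section 9.7 states two incompatible confirmation rules, and its residual irSD class takes in a first progression that is never rescanned. Each such patient would add about 3.1 percentage points to an irRC disease control summary if the denominator were 32, and more if it were smaller. The number of such patients, and so the total effect, cannot be derived from the documents.

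The phase II decision is not affected. This rests on the phase II primary objective in Section 2, which names RECIST 1.1; the endpoint line in Section 9.1 does not itself name the criteria. The defect should be corrected before irRC data are analyzed, but it does not threaten the trial's main conclusion.

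**What to change.** In Section 9.7, delete the discretion sentence and add text such as: *The same classification rule applies to every patient. An irCR or irPR that is not confirmed as defined below is not counted as a response. A first irPD with no later assessment is not classified as irSD and is not counted as disease control; it is counted as irPD.*

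An equally acceptable ending is to report such patients in a separate unconfirmed category outside disease control. Either choice needs a small matching edit: the first is a stated exception to the irPD definition, and the second adds a value to the list in Section 9.6. If irRC disease control is to be reported, define it and its denominator.

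Separately, reconcile the confirmed-progression wording in Section 6.5 (Survival Follow-up) and Section 6.6 footnote m with the unqualified wording in Sections 4.3 and 4.3.2. Which of these should govern management is for the investigators to settle.

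The cost is wording only: no added scans and no change to sample size or decision rule. The one downside is that the irRC response or disease control rate may come out lower.

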### Secondary Objectives (Phase I)

1. To determine the efficacy of ibrutinib in combination with pembrolizumab based on Response Evaluation Criteria in Solid Tumors (RECIST) v1.1
2. To determine the efficacy of ibrutinib in combination with pembrolizumab based on the RECIST based immune-related response criteria (irRC)..
3. To determine overall survival

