## 6.4 Start of every 3rd cycle (Cycle 3, Cycle 6, etc.)

- Radiologic assessment: CT scan or MRI (chest, abdomen, pelvis) with tumor measurement and disease assessment of non-measurable disease according to RECIST 1.1 and irRC criteria (please see Appendix B)
- TSH and free T4
- Carcinoembryonic antigen (CEA)

- [REDACTED]

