### **7.2 Efficacy**

Response and progression will be evaluated using the international criteria proposed by the revised Response Evaluation Criteria in Solid Tumors (RECIST) guideline (version 1.1) (see Appendix B). Changes in the largest diameter (unidimensional measurement) of the tumor lesions and the shortest diameter in the case of malignant lymph nodes are used in the RECIST criteria.

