### **Disease Parameters**

**Measurable disease.** Measurable lesions are defined as those that can be accurately measured in at least one dimension (longest diameter to be recorded) as  $\geq 10$  mm with CT scan, MRI or calipers by clinical exam. All tumor measurements must be recorded in millimeters (or decimal fractions of centimeters).

Note: Tumor lesions that are situated in a previously irradiated area might be considered measurable if the lesion has increased in size since the radiation.

**Malignant lymph nodes.** To be considered pathologically enlarged and measurable, a lymph node must be  $\geq 15$  mm in short axis when assessed by CT scan (CT scan slice thickness recommended to be no greater than 5 mm). At baseline and in follow-up, only the short axis will be measured and followed.

**Non-measurable disease.** All other lesions (or sites of disease), including small lesions (longest diameter  $< 10$  mm or pathological lymph nodes with  $\geq 10$  to  $< 15$  mm short axis), are considered non-measurable disease. Bone lesions, leptomeningeal disease, ascites, pleural/pericardial effusions, lymphangitis cutis/pulmonitis, and abdominal masses (not followed by CT or MRI), are considered as non-measurable.

**Target lesions.** All measurable lesions up to a maximum of 2 lesions per organ and 5 lesions in total, representative of all involved organs, should be identified as **target lesions** and recorded and measured at baseline. Target lesions should be selected on the basis of their size (lesions with the longest diameter), be representative of all involved organs, but in addition should be those that lend themselves to reproducible repeated measurements. It may be the case that, on occasion, the largest lesion does not lend itself to reproducible measurement in

which circumstance the next largest lesion which can be measured reproducibly should be selected. A sum of the diameters (longest for non-nodal lesions, short axis for nodal lesions) for all target lesions will be calculated and reported as the baseline sum diameters. If lymph nodes are to be included in the sum, then only the short axis is added into the sum. The baseline sum diameters will be used as reference to further characterize any objective tumor regression in the measurable dimension of the disease.

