### **Response Criteria Evaluation of Target Lesions**

**Complete Response (CR):** Disappearance of all target lesions. Any pathological lymph nodes (whether target or non-target) must have reduction in short axis to <10 mm.

**Partial Response (PR):** At least a 30% decrease in the sum of the diameters of target lesions, taking as reference the baseline sum diameters.

**Progressive Disease (PD):** At least a 20% increase in the sum of the diameters of target lesions, taking as reference the smallest sum on study (this includes the baseline sum if that is the smallest on study). In addition to the relative increase of 20%, the sum must also demonstrate an absolute increase of at least 5 mm. (Note: the appearance of one or more new lesions is also considered progression.)

**Stable Disease (SD):** Neither sufficient shrinkage to qualify for PR nor sufficient increase to qualify for PD, taking as reference the smallest sum diameters while on study.

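### Section 9.7 sets 50% and 25% irRC cut-offs on an undefined tumor burden, which fit neither the RECIST-based objective nor the single diameters collected

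*Combined protocol and SAP*

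**What the plan says.** **Objective.** The synopsis and Section 2 (Secondary Objectives, Phase I) set out to determine efficacy "based on the RECIST based immune-related response criteria (irRC"). Section 9.1 lists tumour response by RECIST 1.1 and by irRC as a secondary endpoint.

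**Measurement.** Section 7.2 describes "Changes in the largest diameter (unidimensional measurement) of the tumor lesions and the shortest diameter in the case of malignant lymph nodes" as the basis of the RECIST criteria. Appendix B counts a lesion as measurable if it can be measured accurately "in at least one dimension (longest diameter to be recorded"), and for nodes says that "only the short axis will be measured and followed". These diameters are added into one sum. The available text nowhere asks for a second, perpendicular diameter.

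**Where the irRC rules are said to be.** Section 6.4 asks for tumour measurement and disease assessment "according to RECIST 1.1 and irRC criteria (please see Appendix B"). Section 9.6 has both classifications assigned by program at each visit and also refers to Appendix B. That appendix contains RECIST 1.1 only.

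**Cut-offs.** In Appendix B, PR is "At least a 30% decrease in the sum of the diameters of target lesions" from baseline. PD is a 20% rise from the smallest sum, together with an absolute rise of at least 5 mm. In Section 9.7, irPR "is a decrease in tumor burden of greater than or equal to 50% relative to baseline", and irPD is a 25% rise from the minimum with no millimetre floor. Section 9.7 cites a published reference for the immune criteria but does not itself say what tumor burden is.

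**Confirmation.** Section 9.7 leaves confirmation of immune response to the investigator, and then makes it a condition of irCR, irPR and irPD.

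**The concern.** The objective, the measurement and the cut-offs do not fit together. A programmer following Section 9.6 has an undefined variable, one recorded tumour-size quantity, and cut-offs that differ from those Appendix B attaches to that quantity.

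At stake is what the irRC results mean. Two criteria sets reported side by side are useful if their differences reflect how immune response is handled, for example confirmation of progression or the treatment of new lesions. Here some differences would come from the percentage cut-offs alone, on the same scan and the same millimetres, and a reader could take them for an immune response pattern. If the meaning of tumor burden is settled only at analysis, it will be settled in an open-label study after responses are known.

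**Working it through.** The plan gives no figure to reproduce on this point. The check applies the two sets of cut-offs to the same numbers.

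**Inputs**
- S = sum of target-lesion diameters, S0 = its baseline value, Smin = its smallest value on study (Appendix B).
- RECIST 1.1 (Appendix B): PR if S ≤ 0.70 × S0; PD if S ≥ 1.20 × Smin and S − Smin ≥ 5 mm.
- irRC (Section 9.7): irPR if burden ≤ 0.50 × baseline; irPD threshold if burden ≥ 1.25 × minimum.
- Assumption: burden = S, the only size quantity collected. Target lesions alone: no new lesions, no non-target progression, before any confirmation.

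**Step 1. Same sum, S0 = Smin = 100 mm**

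| Change in S | RECIST 1.1 | irRC cut-offs on S |
|---|---|---|
| −55%, −50% | PR | irPR |
| −49%, −40%, −30% | PR | irSD |
| −29% to +19% | SD | irSD |
| +20%, +22%, +24% | PD | irSD |
| +25%, +30% | PD | irPD threshold met |

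The rules disagree for falls of 30% to under 50% and for rises of 20% to under 25%. Elsewhere in this table they agree.

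**Step 2. The 5 mm floor limits the upper band and reverses the direction for small sums**
- 20 to 24 mm is +20% but only +4 mm: RECIST SD and irSD, so the rules agree.
- A rise below 25% can reach 5 mm only if 0.25 × Smin > 5, that is Smin > 20 mm. The whole 20% to under 25% band is RECIST PD once 0.20 × Smin ≥ 5, that is Smin ≥ 25 mm.
- A rise of at least 25% but under 5 mm needs 0.25 × Smin < 5, that is Smin < 20 mm. Example: 16 to 20 mm is +25% and +4 mm. RECIST gives SD, but the irPD threshold is met.

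**Step 3. Does the undefined term matter?** Suppose burden meant a product of two diameters, with both changing in proportion (an assumption), so that area ratio = (diameter ratio)².
- 50% fall in area: √0.50 = 0.707, a 29.3% fall in diameter.
- 25% rise in area: √1.25 = 1.118, an 11.8% rise in diameter.
- A 40% fall in diameter: 0.60² = 0.36, a 64% fall in area. This is irPR on areas but irSD on diameters.
- A 12% rise in diameter: 1.12² = 1.254, a 25.4% rise in area. This meets irPD on areas but is irSD on diameters.

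The two readings classify the same patient differently, and the area reading needs a measurement that the protocol does not collect.

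**Step 4. After the fix.** With burden = S and the Appendix B cut-offs, including the 5 mm floor, the target-lesion rules are identical. Both bands in Step 1 and the small-sum case in Step 2 disappear. What remains comes from confirmation and new-lesion handling.

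**The case against.** The strongest reply is that the plan is under-specified here rather than shown to be misapplied. Nothing says outright that the 50% and 25% cut-offs go on diameter sums. Section 7.2 ties single diameters to RECIST, not to irRC. The objective does not define its RECIST-based label, and the reference cited in Section 9.7 may define tumor burden. This stands in part: use of diameter sums is an inference, and the working states it as an assumption. It does not remove the problem, because the protocol's own cross-references for irRC end in an appendix without irRC rules, and any other quantity would need data that are not collected.

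A second reply is that irRC is meant to differ from RECIST. That is fair for confirmation and new lesions. It does not explain different percentages on the same sum under an objective labelled RECIST-based.

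Three stronger readings are tempting and are not supported:
- *Every patient in the bands is classified differently.* Appendix B requires 5 mm as well as 20% for PD, and its overall-response table makes new lesions or non-target progression PD whatever the target sum does.
- *irRC is always the more lenient rule for progression.* For sums below 20 mm it can be the stricter one, as 16 to 20 mm shows.
- *All differences between the two systems would be artefacts of the cut-offs.* The confirmation and new-lesion rules also separate them.

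**Conclusion.** The point holds as a mismatch within the document. The objective names RECIST-based irRC, only single diameters are recorded, and Section 9.7 sets cut-offs on an undefined quantity that differ from those given for the sum of diameters.

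On target lesions alone, and assuming the cut-offs are applied to that sum, the disagreement is confined to three cases: falls of 30% to under 50%; rises of 20% to under 25% that are also at least 5 mm; and rises of 25% or more that are under 5 mm. The first case changes the response rate but not disease control, since PR and irSD both count as control. The other two change who counts as progressing, the last subject to confirmation. The documents do not allow an estimate of how many patients would fall in these cases.

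A reader might infer that the go/no-go decision is at risk. It is not: the Phase II primary objective names RECIST 1.1, so the rule of at least 1 of 18, then at least 4 of 32, is unaffected as long as RECIST 1.1 is used for it. The consequence is limited to the secondary irRC endpoint, which should be corrected before analysis.

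**What to change.** In Section 9.7:
1. Define irRC tumor burden as the Appendix B sum of diameters.
2. Replace the 50% and 25% cut-offs with those of Appendix B: a 30% decrease for irPR, and a 20% increase together with at least 5 mm for irPD.
3. State how new lesions count towards irRC response and progression. At present they are mentioned only under irCR.
4. Say whether confirmation is mandatory or left to the investigator. The section now says both.

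Also put the irRC rules into Appendix B, or redirect the references in Sections 6.4, 6.5 and 9.6 to Section 9.7.

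The cost is a wording amendment. It uses diameters already collected and concerns only how responses are classified for analysis. Keeping 50% and 25% on some other quantity would cost more: the sponsor would have to define that quantity, collect it, and reword the objective.
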